7.3. Variables

The following variables will be assessed at index date

- Demographic characteristics
 - Age (years)
 - Sex assigned at birth
 - Gender (trans, cis)
 - Race (African American/Black, Asian, White, Other Race)
 - Ethnicity (Hispanic, non-Hispanic)
 - Geographic Region (Northeast, Midwest, South, West, US Territories)
 - Marital status
 - Payer type (Medicaid, Medicare, Commercial insurance, Cash)
- Clinical characteristics
 - Time since first OPERA visit
 - Number of visits with OPERA healthcare provider (HCP) within 12 months prior to baseline
 - Prescriber specialty (MD or DO, physician associate, nurse practitioner, other/unknown)
 - Clinic type (healthcare center, wellness center, other)
- Sexual Behavior and Health
 - History of STI (ever)
 - a) Syphilis
 - b) Gonorrhea

ⁱ The CDC PrEP Clinical Practice Guideline recommends using an STI in the past 6 months as an indication for PrEP. This has been extended to an STI in the past 12 months for this protocol.

ⁱⁱ The National HIV/AIDS Strategy for the United States 2022–2025 identifies youth aged 12-24 as a priority population. This has been changed to individuals aged 18-24 in accordance with the study inclusion criteria Protocol for Non-Interventional Studies PASS Studies and Non-PASS Studies (4.0) March 2024

Template Doc ID: TMF-15706807

Parent Doc ID: VQD-SOP-066694

- c) Chlamydia
- d) Chancroid
- e) Lymphogranuloma venereum
- f) *Mycoplasma genitalium*
- g) Herpes Simplex-2 (HSV-2) infection
- h) Trichomoniasis infection
- i) Human papilloma virus (HPV)/genital warts
- o History of STI (past 3 months)
 - a) Syphilis
 - b) Gonorrhea
 - c) Chlamydia
 - d) Chancroid
 - e) Lymphogranuloma venereum
 - f) *Mycoplasma genitalium*
 - g) HSV-2
 - h) Trichomoniasis infection
 - i) HPV/genital warts

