- Crosstabulation of HIV and STI testing frequency
- STI diagnoses
 - New diagnosis of STI as noted in medical record or positive test result
 - STI diagnoses for
 - Syphilis
 - Gonorrhea
 - Chlamydia
 - Chancroid
 - Lymphogranuloma venereum
 - Mycoplasma genitalium
 - Hepatitis B virus (HBV)
 - Hepatitis C virus (HCV)
 - HSV-2
 - Trichomoniasis
 - HPV and/or genital warts

People who could benefit from PrEP (Obj 6)

HIV testing & STI screening

- HIV testing
 - Frequency and rate (per 100 person years) of HIV tests over 12-month period
 - Type of HIV tests (RNA [quantitative, qualitative], antigen/antibody, rapid screen)
 - HIV testing practices (type, frequency) by HCP type (MD or DO, physician associate, nurse practitioner, other/unknown)
 - HIV testing practices (type, frequency) by clinic type (healthcare center, wellness center, other)
- HIV diagnoses
 - Frequency of new HIV diagnosis and/or detectable HIV RNA and/or positive antigen/antibody test
 - Rate of incident HIV diagnoses per 100 person-years of follow-up
 - Within the first 12 months after index PrEP start
 - Through study end (Analysis #1: 30JUN2024; Analysis #2: 30JUN2025)

- Follow-up (FU) will be censored at first of:
 - HIV diagnosis
 - Death
 - Study end (Analysis #1: 30JUN2024; Analysis #2: 30JUN2025)
 - Loss to follow-up (12 months after last clinical contact)
 - 12 months after index date
- All potential HIV acquisitions will be subject to a thorough chart review for confirmation
 - All lab results, diagnoses, ART prescriptions and clinician notes available in OPERA on or after the potential HIV acquisition was identified will be reviewed
- STI screening
 - Frequency and rate (per 100 person years) of STI testing events (testing for multiple STIs on the same day will count as 1 testing event)
 - Type of other STI tests
 - Syphilis
 - Gonorrhea
 - Chlamydia
 - Chancroid
 - Lymphogranuloma venereum
 - Mycoplasma genitalium
 - Hepatitis B virus (HBV)
 - Hepatitis C virus (HCV)
 - HSV-2
 - Trichomoniasis
 - HPV and/or genital warts
 - Timing of STI tests as recommended by PrEP clinical guidelines⁷
 - Testing 3 months (76-104 days) after last test
 - Testing 6 months (168-196 days) after last test
 - Testing 12 months (351-379 days) after last test
 - STI screening practices (type, frequency) by HCP type type (MD or DO, physician associate, nurse practitioner, other/unknown)
 - STI screening practices (type, frequency) by clinic type (healthcare center, wellness center, other)

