Baseline demographic and clinical characteristics will be described at the first OPERA visit with a PrEP indication, using median and interquartile ranges for continuous variables and counts and proportions for categorical variables. The frequency and rate (per 100 person-years) of HIV testing, HIV diagnoses, STI screening, and STI diagnoses will be described at the first OPERA visit with a PrEP indication and in the 12-months after the first indication.

Characteristics of the tests conducted will also be described. Frequency and type of tests performed will be described by type of healthcare provider ordering the test and clinic type. Rates of HIV tests and diagnoses as well as STI tests and diagnoses over the first 12 months will be estimated using time-updated univariate Poisson regression

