	Oral PrEP N=	CAB LA PrEP N=
HIV testing on schedule (oral: every 3 months (76-104 days); CAB LA: ±14 days of each injection), n (%)		
STI screening every 3 months (76-104 days) ^c , n (%)		
STI screening every 6 months (168-196 days) ^d , n (%)		
STI screening every 12 months (351-379 days) ^e , n (%)		
HIV testing NOT on schedule (oral: every 3 months (76-104 days); CAB LA: ±14 days of each injection), n (%)		
STI screening every 3 months (76-104 days) ^c , n (%)		
STI screening every 6 months (168-196 days) ^d , n (%)		
STI screening every 12 months (351-379 days) ^e , n (%)		

\$(vault:document_date__v)

Protocol for Non-Interventional Studies PASS Studies and Non-PASS Studies (4.0) March 2024

Template Doc ID: TMF-15706807

Parent Doc ID: VQD-SOP-066694

Table 26. STI diagnoses among PrEP users^a

	Oral PrEP N=	CAB LA PrEP N=
STI diagnosis within 14 days before/on day of PrEP type start, n (%)		
Any, n (%)		
Syphilis, n (%)		
Gonorrhea, n (%)		
Chlamydia, n (%)		
Chancroid, n (%)		
Lymphogranuloma venereum, n (%)		
Mycoplasma genitalium, n (%)		
Herpes Simplex-2, n (%)		
Trichomoniasis, n (%)		
Human papilloma virus/genital warts, n (%)		
HBV, n (%)		
HCV, n (%)		
STI diagnosis within 12 months after PrEP type start, n (%)		
Any, n (%)		
Syphilis, n (%)		
Gonorrhea, n (%)		
Chlamydia, n (%)		
Chancroid, n (%)		
Lymphogranuloma venereum, n (%)		
Mycoplasma genitalium, n (%)		
Herpes Simplex-2, n (%)		
Trichomoniasis, n (%)		
Human papilloma virus/genital warts, n (%)		
HBV, n (%)		
HCV, n (%)		

^a Tests are only counted for the PrEP type used at the time of diagnosis

Table 27. Incidence rate of STI diagnoses within 12 months of index among PrEP users^a

	Oral PrEP N=	CAB LA PrEP N=
Total # STI diagnoses within 12 months of index, n		
Person-years of follow-up		
IR per 100 py (95% CI)		

Table 28. Identification of the people who could benefit from PrEP population

	Included N (%)	Excluded N (%)
All individuals in OPERA		
≥1 clinical encounter between 21DEC2021 and 30JUN2023		
≥18 years old at first clinical encounter in study period		
Any indication for PrEP ^a		
No PrEP use between 21DEC2021 and 30JUN2023		

^a Bacterial STI in past 12 months (gonorrhea, syphilis, chlamydia), alcohol use disorder, illicit non-injection drug use, injection drug use. Black woman, transgender woman, men who have sex with men, aged 18-24 years, any history of PrEP use

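### Section 7.3.2 does not say when a positive STI test is new, so the pooled STI incidence rates in Annex 1 Tables 27 and 43 can mix new infections with old or repeatedly positive ones

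*Protocol*

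**What the plan says.** Section 7.3.2 of the Protocol defines the STI diagnosis outcome in one line: "New diagnosis of STI as noted in medical record or positive test result". The same line is used for PrEP users (Objective 5) and for people who could benefit from PrEP (Objective 6). A list of 11 infections follows. Seven are curable: syphilis, gonorrhea, chlamydia, chancroid, lymphogranuloma venereum, *Mycoplasma genitalium* and trichomoniasis. Four are viral and can persist: HBV, HCV, HSV-2 and "HPV and/or genital warts".

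The rate of STI diagnoses belongs to Objective 5 as worded in Section 6. For Objective 6, Section 7.7.1.1 plans Poisson regression for "Rates of HIV tests and diagnoses as well as STI tests and diagnoses over the first 12 months". Annex 1 Table 27 is titled "Incidence rate of STI diagnoses within 12 months of index among PrEP users". Its numerator row is "Total # STI diagnoses within 12 months of index, n", set over person-years. Table 43 has the same rows for Objective 6. Neither table splits by infection. Tables 26 and 42 do, as n (%).

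STI history (ever, and past 3 months) is a baseline variable in Section 7.3 and in Annex 1 Tables 8 and 32. Those lists hold nine infections. HBV and HCV are absent, although both are outcomes.

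**The concern.** An incidence rate needs a rule for what counts as a new event and who is still at risk of one. Section 7.3.2 gives neither for STIs. It sets no look-back, no exclusion of people with an earlier diagnosis or positive, no qualifying test type (antibody or active infection), and no interval that turns two positives into two episodes. Baseline STI history is described but not linked to the outcome.

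For an infection whose marker stays positive for years, a test during follow-up can therefore add an event although nothing new happened, and a second test can add another. Three features of the design make this more likely to matter:

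- Objective 6 admits people because of a bacterial STI, syphilis included, in the past 12 months. The qualifying infection may still test positive after index.
- Table 26 has one window up to PrEP start and one after it, with no rule that keeps one infection out of both.
- People who switch PrEP type contribute to both columns, so one old infection could be counted under each.

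At stake is the meaning of the two pooled rates, and whether two programmers working from this text would produce the same number.

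**Working it through.** **The plan's own figures.** There are none to reproduce. The protocol states no expected STI rate, event count or retest frequency. Its precision table in Section 7.5 concerns proportions.

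**Rules the protocol does set at this level.** Section 7.3.2 merges STI tests done on the same day, but only for screening events. It requires chart review of potential HIV diagnoses. It sets no comparable rule for STI diagnoses.

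**Illustration.** Every input here is an assumption, as is the premise that some markers stay positive. For people followed for a full year, let λ be the true new-infection rate per 100 person-years over everyone, π the share already persistently positive, and k the tests per person-year in those people. Three ways to apply the text are:

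- A, every positive counts: λ + 100·π·k
- B, one count per person, no look-back: λ + 100·π (each carrier tested at least once)
- C, first positive only, earlier recorded positives removed from numerator and person-time: λ / (1 − π) (all carriers already recorded)

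For a rare persistent infection with λ = 1:

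| π | k | A | Old share of A | B | C |
|---|---|---|---|---|---|
| 0.02 | 1 | 1 + 2 = 3 | 2/3 = 67% | 1 + 2 = 3 | 1/0.98 = 1.02 |
| 0.10 | 2 | 1 + 20 = 21 | 20/21 = 95% | 1 + 10 = 11 | 1/0.90 = 1.11 |
| 0.20 | 4 | 1 + 80 = 81 | 80/81 = 99% | 1 + 20 = 21 | 1/0.80 = 1.25 |

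For a pooled rate as in Tables 27 and 43, take λ = 50 new infections of all kinds per 100 person-years under A:

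- π = 0.02, k = 1: 50 + 2 = 52, of which 2/52 = 4% is old.
- π = 0.20, k = 4: 50 + 80 = 130, of which 80/130 = 62% is old.
- π = 0, or k = 0: 50, with no distortion.

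The distortion therefore runs from nothing to more than half of the pooled count, depending on inputs the protocol does not give. In the middle row of the table, the same data give 21, 11 or about 1 per 100 person-years according to how the one-line definition is read.

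**The case against.** The strongest reply is that the word new can govern both routes in the definition, so that a positive test counts only when it marks a new diagnosis. That reading is fair. A reader might infer that any positive test counts; the text does not compel this. What remains is that newness is never defined for a test result, so the better reading cannot be programmed from the text.

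Second, look-back and episode rules often sit in the SAP, and Section 7.8 says analysis specifications hold definitions of key variables. Silence alone would not be a finding. Here, however, the protocol itself fixes the outcome rule, the incidence label and the pooled numerator.

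Third, Tables 26 and 42 show each infection separately as n (%) of people. Repeat positives should not inflate those counts, and readers can see the curable infections apart. This stands, although an old positive can still place a person in the count once.

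Fourth, the study is descriptive (Sections 7.3.3 and 7.7), and no formal contrast of STI rates is planned. This also stands, but a descriptive incidence rate still needs a definition of an incident event.

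Two further inferences go too far. One is that the rates do not measure new STIs at all. For gonorrhea, chlamydia, trichomoniasis and similar infections most positives mark current infection, and the gap is mainly the episode rule, so the rates mix old and new. The other is that visits every 2 rather than 3 months would produce a spurious LA-to-oral rate ratio of 6/4 = 1.5. Those intervals, in Section 5, are for HIV tests. The STI intervals in Section 7.3.2 (3, 6 and 12 months) do not differ by PrEP type, and nothing says that people known to be positive are retested at each injection visit.

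**Conclusion.** The point holds in a limited form. As written, the STI diagnosis rule leaves new undefined for test results and allows prevalent and repeated positives into Tables 27 and 43, which are labelled incidence rates. Exposure is greatest for HSV-2, HBV, HCV, HPV and previously treated syphilis. It is smaller for the other curable infections and for the n (%) in Tables 26 and 42.

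The size cannot be established from the protocol. The added 2 to 80 events per 100 person-years rests on an assumed carrier share of 2% to 20% and 1 to 4 tests a year in carriers, and falls to zero if carriers are not retested. No claim is made about a difference between oral and LA PrEP. The definition should be amended because the rate serves Objectives 5 and 6 in both planned analyses.

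**What to change.** In Section 7.3.2, for both populations:

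1. For HSV-2, HBV, HCV and HPV, count only the first diagnosis or positive result after index in people with no earlier diagnosis or positive in the record. Limit person-time to those still at risk of that infection. Add HBV and HCV to the baseline history in Section 7.3 and in Annex 1 Tables 8 and 32.
2. For curable STIs, count one episode per prespecified interval. Do not count a positive treponemal test alone after earlier syphilis.
3. In Annex 1 Tables 27 and 43, report the rate for curable STIs separately from the rate for persistent viral infections.

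The cost is definition wording and a look-back in data already held. There are two downsides. Some true reinfections inside the interval will be merged. And because look-back is often short (Section 7.4 gives average follow-up of 1.2 years), a first recorded positive may still be a long-standing infection. Section 7.9 should state that as a limitation.

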5. Assess HIV testing and STI screening patterns at index oral or LA PrEP initiation and within 12-months following index PrEP initiation among people who initiate a PrEP regimen
6. Describe demographic and clinical characteristics, HIV testing and diagnoses, as well as STI screening and diagnoses over a 12-month period of follow-up among people who are not on PrEP but could benefit from PrEP

Study Design

Design: Cohort study using secondary data from electronic medical records in the OPERA cohort.

Exposure groups: Oral PrEP, LA PrEP

Duration of study:

- Analysis #1: 2021 to 2023 (Obj 1-1a); 21DEC2021 to 30JUN2024 (Obj 2-6)
- Analysis #2: 2021 to 2024 (Obj 1-1a); 21DEC2021 to 30JUN2025 (Obj 2-6)

Population

(Obj 1) People in OPERA aged ≥ 18 years with ≥ 1 clinical encounter during the calendar year of interest and no evidence of prior HIV diagnosis.

(Obj 1a) People with an incident HIV diagnosis identified in Obj 1.

(Obj 2-5) People without HIV in OPERA aged ≥ 18 years who initiated any new PrEP formulation during the study period with or without prior PrEP use.

(Obj 6) People without HIV in OPERA aged ≥ 18 years who could benefit from PrEP and are not on PrEP

Variables

Exposures:

- PrEP use (never, use within ≤ 12 months before diagnosis, use > 12 months before diagnosis)
- Time-updated PrEP type (oral or LA)

Outcomes:

- Incident HIV diagnosis: New HIV diagnosis *and/or* detectable HIV RNA *and/or* positive antigen/antibody test
- PrEP coverage: Proportion of days of access to oral PrEP or proportion of days of coverage by CAB LA
- HIV testing/STI screening: frequency and type of tests performed

Data Sources

OPERA cohort, a multi-site observational database built from the complete patient health records managed in electronic health record (EHR) systems throughout the US.

Study Size

Between 21DEC2021 and 30JUN2023 (Analysis # 1 inclusion period), 22,234 adults without HIV started a new PrEP formulation in OPERA. The first formulation used during the study period was TAF/FTC oral (n=12,110, 54%), TDF/FTC oral (n=9,740, 44%), or CAB LA (n=384, 2%). An additional 292 individuals switched to CAB LA PrEP later during the study period, for a total of 767 people receiving CAB LA injections during the Analysis #1 inclusion period.

Protocol for Non-Interventional Studies PASS Studies and Non-PASS Studies (4.0) March 2024

Template Doc ID: TMF-15706807

Parent Doc ID: VQD-SOP-066694

Data Analysis

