7. RESEARCH METHODS

7.1. Study Design

A cohort study using secondary data from the OPERA[®] (Observational Pharmacology Epidemiology Research & Analysis) cohort will be used to answer the study objectives. OPERA is a multi-site observational database collecting data prospectively from the complete electronic health records (EHR) from clinical care throughout the US.

[figure not shown]
Analyses to meet the study objectives will be conducted twice during the study period. Analysis #1 will include data from 01JAN2021-31DEC2023 (Obj. 1-1a) and from 21DEC2021 to 30JUN2024 (Obj 2-6). Analysis #2 will be a repeat of Analysis #1 with data from 1JAN2021-31DEC2024 (Obj. 1-1a) and from 21DEC2021 to 30JUN2025 (Obj 2-6). A

summary of the study design is provided in Table 1 (exposure groups, index date, censoring criteria, endpoints) and in Figure 1 (timeline).

Table 1. Summary of study design

		Analysis #1	Analysis #2
Obj 1 Among all people without HIV in OPERA	Exposure groups	Calendar years	Calendar years
	Index date	NA	NA
	Censoring criteria	NA	NA
	Endpoints	HIV diagnosis	HIV diagnosis
Obj 1a Among people with a new HIV diagnosis	Exposure groups	PrEP use (never, use within ≤12 months before diagnosis, use >12 months before diagnosis)	PrEP use (never, use within ≤12 months before diagnosis, use >12 months before diagnosis)
	Index date	Date of HIV diagnosis	Date of HIV diagnosis
	Censoring criteria	NA	NA
	Endpoints	NA	NA
Obj 2-5 Among PrEP users	Exposure groups	Oral PrEP, CAB LA PrEP	Oral PrEP, CAB LA PrEP
	Index date	Start of first PrEP regimen during the study period	Start of first PrEP regimen during the study period
	Censoring criteria	Death, loss to follow-up (12 months after last clinical contact), study end (30JUN2024), 12 months after index date	Death, loss to follow-up (12 months after last clinical contact), study end (30JUN2025), 12 months after index date
	Endpoints	HIV diagnosis, PrEP coverage, HIV testing, STI screening, STI diagnoses	HIV diagnosis, PrEP coverage, HIV testing, STI screening, STI diagnoses
Obj 6 Among people who could benefit from PrEP	Exposure groups	NA	NA
	Index date	First OPERA visit with indication for PrEP during study period	First OPERA visit with indication for PrEP during study period
	Censoring criteria	Death, loss to follow-up, study end (30JUN2024), 12 months after index date, PrEP initiation	Death, loss to follow-up, study end (30JUN2025), 12 months after index date, PrEP initiation

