	People who could benefit from PrEP N=
HIV test within 14 days before/on day of PrEP type start, n (%)	
Test type	
RNA only, n (%)	
Quantitative RNA test, n (%)	
Qualitative RNA test, n (%)	
Ag/Ab only, n (%)	
Rapid test only, n (%)	
Both RNA and Ag/Ab, n (%)	
Quantitative RNA test, n (%)	
Qualitative RNA test, n (%)	
Both RNA and rapid test, n (%)	
RNA, Ab/Ag and rapid tests, n (%)	
Days from test to PrEP type start, median (IQR)	
Any HIV test within 12 months after PrEP type start, n (%)	
Total number of testing events ^b , N	
Test type	
RNA only, n (%)	
Quantitative RNA test, n (%)	
Qualitative RNA test, n (%)	
Ag/Ab only, n (%)	
Both RNA and Ag/Ab, n (%)	
Quantitative RNA test, n (%)	
Qualitative RNA test, n (%)	
Number of HIV testing events ^b per person, median (IQR)	
Average testing interval per person (#testing events /weeks on PrEP type), median (IQR)	
Testing on schedule (every 3-6 months (76-196 days)), n (%)	

^b Multiple HIV tests on the same day count as one testing event

Table 34. Incidence rate of HIV testing events and HIV diagnosis within 12 months of index among people who could benefit from PrEP

	People who could benefit from PrEP N=
Total # HIV testing events within 12 months of index, n	
Person-years of follow-up	
IR per 100 py (95% CI)	

Table 35. Incident HIV^a within 12 months of index among people who could benefit from PrEP

	Oral PrEP N=
HIV diagnosis, n (%)	
Months from start of PrEP type to HIV diagnosis, median (IQR)	
Negative HIV test within 2 weeks before/on start of PrEP type, n (%)	
Person-years of follow-up	
IR per 100 py (95% CI)	

Table 36. Frequency and type of HIV tests among people who could benefit from PrEP, by healthcare provider type^a

	MD or DO	Physician Associate	Nurse Practitioner	Other/unknown
Total number of HIV testing events ^b ordered				
Test type				
RNA only, n (%)				
Quantitative RNA test, n (%)				
Qualitative RNA test, n (%)				
Ag/Ab only, n (%)				
Rapid test only, n (%)				
Both RNA and Ag/Ab, n (%)				
Quantitative RNA test, n (%)				
Qualitative RNA test, n (%)				
Both RNA and rapid test, n (%)				
RNA, Ab/Ag and rapid tests, n (%)				
Testing 3-6 months (76-196 days) after last test, n (%)				

^a Assessed at the test-level

^b Multiple HIV tests on the same day count as one testing event

Table 37. Frequency and type of HIV tests within 12 months of index among people who could benefit from PrEP, by clinic type^a

	Healthcare Center	Wellness Center	Other

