Total number of HIV testing events ^b ordered			
Test type			
RNA only, n (%)			
Quantitative RNA test, n (%)			
Qualitative RNA test, n (%)			
Ag/Ab only, n (%)			
Rapid test only, n (%)			
Both RNA and Ag/Ab, n (%)			
Quantitative RNA test, n (%)			
Qualitative RNA test, n (%)			
Both RNA and rapid test, n (%)			
RNA, Ab/Ag and rapid tests, n (%)			
Testing 3-6 months (76-196 days) after last test, n (%)			

^a Assessed at the test-level

^b Multiple HIV tests on the same day count as one testing event

Table 38. STI screening among people who could benefit from PrEP

	People who could benefit from PrEP N=
STI screening within 14 days before/on day of PrEP type start, n (%)	
STI tested, n (%)	
Syphilis	
Gonorrhea	
Chlamydia	
Chancroid	
Lymphogranuloma venereum	
Mycoplasma genitalium	
Herpes Simplex-2	
Trichomoniasis	
Human papilloma virus/genital warts	
HBV	
HCV	
Days from test to PrEP type start, median (IQR)	
Any STI screening within 12 months after PrEP type start, n (%)	
Number of STI screening events ^b , median (IQR)	
Syphilis, n (%)	
Gonorrhea, n (%)	
Chlamydia, n (%)	
Chancroid, n (%)	
Lymphogranuloma venereum, n (%)	
Mycoplasma genitalium, n (%)	
Herpes Simplex-2, n (%)	
Trichomoniasis, n (%)	
Human papilloma virus/genital warts, n (%)	
HBV, n (%)	
HCV, n (%)	
Average screening interval per person (# screening events/weeks on PrEP type), median (IQR)	
Testing every 3 months ^c , n (%)	
Testing every 6 months ^d , n (%)	
Testing every 12 months ^e , n (%)	

^a Tests are only counted for the PrEP type used at the time of diagnosis

^b Multiple STI tests on the same day count as one screening event

^c Recommended gonorrhea, chlamydia and syphilis screening interval for MSM and transgender women who have sex with men

^d Recommended gonorrhea and syphilis screening interval for heterosexual women and men

^e Recommended chlamydia screening interval for heterosexual women and men

Table 39. Incidence rate of STI screening events within 12 months of index among people who could benefit from PrEP

	People who could benefit from PrEP N=
Total # STI screening events within 12 months of index, n	
Person-years of follow-up	
IR per 100 py (95% CI)	

Table 40. Frequency and type of STI screening among people who could benefit from PrEP, by healthcare provider type^a

	MD or DO	Physician Associate	Nurse Practitioner	Other/unknown
Total number of STI screening events ^b ordered				
STI tested, n (%)				
Syphilis				
Gonorrhea				
Chlamydia				
Chancroid				

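### Objective 6 HIV-diagnosis rule in section 7.3.2 uses a PrEP-start clock and omits censoring at PrEP initiation, contradicting Table 1; several Annex shells carry the same PrEP-user wording

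*Protocol*

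**What the plan says.** The synopsis defines the Objective 6 population as "People without HIV in OPERA aged ≥ 18 years who could benefit from PrEP and are not on PrEP". Table 1 in section 7.1 sets the index date as "First OPERA visit with indication for PrEP during study period" and, for Analysis #1, censors at "Death, loss to follow-up, study end (30JUN2024), 12 months after index date, PrEP initiation". Analysis #2 has the same events with the later study end.

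Section 7.3.2, under HIV diagnoses for Objective 6, asks for the rate "Within the first 12 months after index PrEP start" and also for a rate through study end. Its censoring list has five items: HIV diagnosis, death, study end, "Loss to follow-up (12 months after last clinical contact") and 12 months after index. PrEP initiation is not among them. For HIV tests, STI screening and STI diagnoses, section 7.3.2 gives no Objective 6 censoring list.

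The Objective 6 shells in Annex 1 include these rows:
- Table 33: "Any HIV test within 12 months after PrEP type start, n"
- Table 35: "Months from start of PrEP type to HIV diagnosis, median (IQR")
- Table 38: "Average screening interval per person (# screening events/weeks on PrEP type), median (IQR")

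Table 35 has a single column headed for oral PrEP. Table 43 has one column for oral PrEP and one for CAB LA.

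**The concern.** The protocol fixes two time origins and two censoring rules for the same HIV rate. A programmer working from section 7.3.2 would produce a different quantity from one working from Table 1. Under section 7.3.2, someone who starts PrEP during follow-up keeps contributing person-time and diagnoses to a rate meant to describe people off PrEP. Read literally, the clock is worse: it is undefined for those who never start PrEP, and for those who do it begins on the day Table 1 ends their follow-up.

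The shells have the same fault. A window around the start of a PrEP type, or a denominator of weeks on that type, has no sensible value for a person who stays off PrEP.

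**Working it through.** **Text comparison (Objective 6)**

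| Item | Table 1, section 7.1 | Section 7.3.2, HIV diagnoses | Section 7.7.1.1 |
|---|---|---|---|
| Clock starts | First visit with an indication | Index PrEP start | First visit with an indication |
| Ends at PrEP initiation | Yes | Not listed | Not mentioned |
| Length | 12 months | 12 months and through study end, but censored at 12 months | 12 months |

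The section 7.3.2 windows and five-item list match the PrEP-user block (Objectives 2-5) of the same section item for item, which points to carried-over text. The through-study-end rate cannot differ from the 12-month rate while the 12-month cut-off is in the list. Neither the objective nor Table 35 asks for it.

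**Who could contribute time on PrEP**

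Annex Table 28 removes anyone with PrEP use from 21DEC2021 to 30JUN2023. Follow-up for Analysis #1 can run to 30JUN2024 (Figure 1 notes), so PrEP starts after 30JUN2023 remain. For example, a person indexed on 15JUN2023 who starts PrEP on 15AUG2023 passes the filter and, under section 7.3.2, contributes about 2 months off PrEP and 10 months on it. The Objective 6 criteria in section 7.2.1 do not contain this filter, so the unfiltered case is shown too.

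**Size**

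The protocol gives no expected rate or uptake for Objective 6, so there is no figure to reproduce. Assumptions: index dates uniform over the 557 days of the inclusion period, 365 days of follow-up, no death or loss, and constant PrEP uptake h per year, so the daily hazard is λ = −ln(1−h)/365.

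Without the filter, everyone is exposed for 365 days:

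On-PrEP share = 1 − h/[−ln(1−h)]

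For h = 0.05 this is 1 − 0.05/0.0513 = 0.025.

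With the filter, only follow-up after 30JUN2023 is exposed. That concerns 365/557 = 66% of people and (365 × 366/2)/(557 × 365) = 183/557 = 33% of person-time:

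On-PrEP share = Σ[T − (1−e^(−λT))/λ]/(557 × 365), summed over T = 1 to 365 days

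To illustrate the HIV rate, section 5 cites a relative risk of 0.24 for PrEP against non-PrEP controls. The blended rate relative to the off-PrEP rate is 1 − share × (1 − 0.24).

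| Assumed uptake per year | On-PrEP share, no filter | HIV rate ratio | On-PrEP share, Table 28 filter | HIV rate ratio |
|---|---|---|---|---|
| 5% | 2.5% | 0.98 | 0.6% | 0.996 |
| 10% | 5.1% | 0.96 | 1.1% | 0.991 |
| 20% | 10.4% | 0.92 | 2.3% | 0.982 |

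With Table 1's rule, the on-PrEP share is zero by construction. The ratios reflect protection only and ignore any change in detection.

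**The case against.** The strongest reply is that Table 1 already has the right rule. It is presented as the summary of index dates and censoring, it applies to both analyses, section 7.7.1.1 uses the same clock, and several Objective 6 shell titles count from index. A clock at PrEP start cannot be run for people who never start, so a competent programmer would recognise copied text and follow Table 1. This stands to the extent that bias arises only if section 7.3.2 is followed. It does not remove the contradiction, because section 7.3.2 is where the outcome is defined.

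A reader might infer that HIV testing and STI rates are contaminated in the same way. The document does not support that. The conflicting list sits under HIV diagnoses only; for the other outcomes section 7.3.2 is silent, and Table 1, which does censor at PrEP initiation, is the only rule.

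A reader might also infer a large distortion. With Table 28 applied, the share of time on PrEP is a few percent at most over the uptake range shown. Index is the first qualifying visit in the period, so real index dates probably fall earlier than the uniform assumption, which lowers the share further. The dated example is close to the worst case.

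Finally, a reader might infer that the HIV rate must be understated. Section 7.9 notes that diagnoses are found only when tests are done, and section 5 says an HIV test is required before PrEP starts. Starting PrEP can therefore reveal existing infections as well as prevent new ones, and the net direction is not certain.

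**Conclusion.** The contradiction is real and is wrong as written. For Objective 6, the HIV-diagnosis rule in section 7.3.2 has the wrong time origin, lacks the censoring event given in Table 1, and pairs a through-study-end rate with a 12-month cut-off. Tables 33, 35, 38 and 43 cannot be filled sensibly for people not on PrEP. These faults in the text hold whatever the uptake.

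The numerical consequence is conditional and probably small: about 0.6% to 2.3% of person-time on PrEP with the Table 28 filter, or about 2.5% to 10% without it, at 5% to 20% uptake per year. Uptake, uniform index dates and absence of loss are assumptions. No direction for the diagnosed-HIV rate should be claimed.

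**What to change.** In section 7.3.2, Objective 6:
- Set the HIV-rate window to 12 months after the first OPERA visit with a PrEP indication.
- Add PrEP initiation to the censoring list, and state that the list applies to HIV tests, HIV diagnoses, STI screening and STI diagnoses.
- Drop the through-study-end rate, or reconcile it with the 12-month cut-off.

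In Annex 1:
- Tables 33, 35 and 38: replace the PrEP-start wording with the Objective 6 index date.
- Tables 33 and 38: replace weeks on PrEP type with weeks of censored follow-up.
- Tables 35 and 43: use one column for people who could benefit from PrEP.

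The cost is text and table-shell edits. PrEP prescription and injection dates are already in the data source. Any loss of person-time is slight and is limited to time that Table 1 already excludes.
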